#### **6.e. Data Safety Monitoring Plan**

[name] of the Department of Psychiatry and Health Behavior will serve as the internal Medical Monitor for this study. [name] will have no other relationship with this study or any other study on which [name] is the principal investigator. All serious adverse events (SAEs) will be reported immediately to [name]. Otherwise [name] will review the case report forms for the Scale for Suicide Ideation, vital signs, and AEs after the third and sixth patients are completed.

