### METHODS OF THE PRESENT PROPOSAL

#### 3.e.2. OVERVIEW

This pilot study will enroll 20 participants with PTSD who have prominent problem with nightmares and a mild-to-moderate degree of suicidality. Participants will have been on a stable dose of an SSRI or open label treatment for bipolar disorder, at a therapeutic dose, for at least one month before baseline assessment. Patients with bipolar disorder will have been on a stable dose of FDA-approved treatment for bipolar disorder

(lithium, valproic acid, lamotrigine, quetiapine, asenapine, olanzapine, ziprasidone, lurasidone or the olanzapine-fluoxetine combination). Patients who meet all qualifying requirements at baseline will then be randomized in a 1:1 proportion to either prazosin 1 mg at bedtime or placebo. Over the course of 6 weeks, the dose of prazosin will be increased as tolerated, while the dose of the SSRI or medication for bipolar disorder is held constant. Participants will be re-assessed weekly for 8 weeks post-randomization, and only enough prazosin will be provided to last until the next visit.

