#### **6.d. Safeguards**

The Star\*D trial was among the first NIH-sponsored trials to follow the 2001 NIH guidelines for studies which included patients at risk of suicide. <http://www.nimh.nih.gov/health/topics/suicide-prevention/issues-to-consider-in-intervention-research-with-persons-at-high-risk-for-suicidality.shtml> {Nierenberg, 2004 924 /id} The guidelines have several stipulations, and we have responded accordingly:

- 1) "Provide specific inclusion criteria and their measurement with regards to suicidality"

Response: Patients included in the study will have a Scale for Suicidal Ideation (SSI) scores  $\geq 3$  but with C-SSRS suicidal ideation scores of  $\leq 3$ . This range defines patients with mild and moderate suicidal ideation, but with no intent to commit suicide. This inclusion range for suicidal ideation is consistent with prior clinical trials of suicidal patients. {Brown, 2005 1468 /id; Grunebaum, 2012 1470 /id}

"Specify the criteria for withdrawal from the treatment trial with regard to increased suicidality, increased related symptoms, lack of treatment response, and treatment side effects, and what alternative treatment or referral will be offered."

Response: The decision to withdraw the participant from research treatment will be based upon either the participant's view or the research psychiatrist's opinion that the patient is experiencing severe suffering, is at imminent risk for suicide, or is functionally decompensating. The clinician's opinion will be informed on the basis of the DDNSI, the PCL-S, and the C-SSRS, but the decision to withdraw a participant will be based upon a combination of psychometrics along with global clinical judgment. If a participant is withdrawn from the study, then he or she will be offered care-as-usual, or hospitalization if necessary.

- 2) "Consider and establish criteria for hospitalization, where the hospitalization will take place, and the procedures within the hospital that provide additional safety"

Response: Hospitalization will be offered if the patient is judged at imminent risk of suicide, is functionally decompensated, or needs specialized treatment outside of the protocol (such as ECT), according to the global clinical judgment of the study psychiatrist. Hospitalization would take place in the inpatient units of Georgia Regents Medical Center, or East Central Regional Hospital, or similar regional facility.

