- 3) "Describe procedures in the protocol for managing increases in suicidality, and how research staff is trained and available to provide clinical management"

Response: Managing increases in suicidality is predicated upon detection of such increases. Although we proposed to examine participants weekly, we recognize that suicidal ideation may emerge suddenly and unpredictably. Therefore, research staff will make at least one mid-week phone call to each participant for the first 2 weeks to check on their well-being and assure them that the study staff is available. At each scheduled study visit, the protocol will quantify suicidality 2 ways. First, the participant will complete the

Scale for Suicide Ideation. This information flows from the research staff to study psychiatrists at the time of the visit. Second, the research psychiatrist will administer the Columbia Suicide Severity Rating Scale (C-SSRS), allowing for a thorough review for the presence of any self-injurious behavior since the last visit or the development of any preparatory suicidal planning, as categorized by the C-SSRS.{Oquendo, 2003 1195 /id} Patients judged by the study psychiatrist to be at increased risk of suicide will have an increased frequency of research visits, have smaller supplies of research medication, or may be withdrawn from the study and possibly hospitalized.

- 4) "Have a procedure for emergency coverage that is clearly understood by the clinical research staff, study participants, and families"

**Response:** At the time of consent, participants will receive clear instructions for how to reach study staff during the daytime, and how to access after-hours coverage as provided through each site. Psychiatry residents-in-training who receive emergency calls from participants after-hours will be instructed to call the local principal investigator immediately, regardless of the time of day. The PI or designated co-I will be continuously available to the respective on-call residents to guide crisis management and assess for the primary suicidal endpoints, if necessary by phone.

- 5) "As part of the consent process, consider having explicit discussion with relevant family members, guardians, or friends that includes the risks inherent when study participants are suicidal (risk of death, side effects of treatment)"

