**Response:** Involvement of the participant's family will be encouraged, starting by asking potential participants to bring their families to the first face-to-face screening visit.

- 6) "Consider and identify the limits of confidentiality with respect to suicidality, as well as other circumstances"

**Response:** When a participant has emergent suicidality defined as an increase of 6-points (one standard deviation of SSI scores in [name] outpatients), we will inform the participant of our intent to share this with the relevant family, and the consent form will reflect this.

- 7) "Consider the impact of suicidality on the study participant's capacity to give informed consent"

**Response:** Consent will be obtained only from persons who normally would not meet criteria for emergent psychiatric hospitalization, i.e., C-SSRS suicidal ideation score < 4.

- 8) "Determine whether additional safeguards are needed to ensure the safety of the study participants"

**Response:** No additional safeguards needed

- 9) "Consider situations in which a trial would be terminated prematurely"

**Response:** As this is a pilot study with only 20 participants, we have no statistical endpoints for early termination of the study. However, the trial would be terminated prematurely only if the Medical Monitor determined that there was a systematic increase in risk, according to the Data Safety Monitoring Plan,

below.

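### No Medical Monitor review of SSI, vital-sign or adverse event forms is scheduled after the sixth completed patient of 20, although the Monitor's finding is the only stated ground for ending the trial early

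*Combined protocol and SAP*

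**What the plan says.** Section 3.e.2 sets the size and length of the trial: "This pilot study will enroll 20 participants with PTSD", and "Participants will be re-assessed weekly for 8 weeks post-randomization".

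Section 6.e gives the Medical Monitor two inputs. The first has no patient-number limit: "All serious adverse events (SAEs) will be reported immediately to" the Monitor. The second is a scheduled look at forms: the Monitor "will review the case report forms for the Scale for Suicide Ideation, vital signs, and AEs after the third and sixth patients are completed". No later look, repeating interval or closing review is stated.

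Section 6.d, item 9, says that there are no statistical endpoints for early termination and that "the trial would be terminated prematurely only if the Medical Monitor determined that there was a systematic increase in risk", judged according to the plan in 6.e.

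Safeguards for the individual do not stop at the sixth patient. On SSI results, 6.d, item 3, says "This information flows from the research staff to study psychiatrists at the time of the visit", and adds: "Patients judged by the study psychiatrist to be at increased risk of suicide will have an increased frequency of research visits". Smaller drug supplies, withdrawal or hospitalization are also possible. On withdrawal, 6.d, item 1, says that "the decision to withdraw a participant will be based upon a combination of psychometrics along with global clinical judgment".

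**The concern.** A rise in risk that is systematic is a pattern across participants. The plan makes one person's judgment of that pattern the stated ground for ending the trial, and it names the forms that person should see. The scheduled supply of those forms then ends at the sixth completer.

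The forms match the trial's own named risks. Section 6.c calls orthostatic hypotension the primary risk of prazosin, and 6.h.1 defines emergent suicidal ideation as a 6-point increase. Under 6.d, item 6, such an increase leads to telling the participant that it will be shared with family. No section sends it to the Monitor unless it is also a serious adverse event. A run of moderate SSI rises, low blood pressure readings or non-serious events among later participants could therefore be handled well one by one and never be put together in front of the Monitor.

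Section 6.e also leaves two things open: whether a withdrawn participant counts as completed, and whether a review covers forms from participants who were withdrawn or are still in treatment.

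**Working it through.** **Inputs.** Planned size 20 and 8 weeks of treatment (3.e.2); form reviews after 3 and 6 completed patients (6.e); no accrual or dropout rate anywhere. The schedule is itself the stated figure, so there is no derived number to reproduce.

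**1. Direct count.** Completed at the last scheduled review: 6/20 = 30%. Finishing later: 20 − 6 = 14, and 14/20 = 70%. If *w* participants are withdrawn before the sixth completes (assumed), 14 − *w* remain: 13 (65%), 12 (60%) or 11 (55%) for *w* = 1, 2 or 3.

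**2. Why 14 is a ceiling.** Assume one entry every *d* weeks and no withdrawals. The sixth participant starts at week 5*d* and finishes at week 5*d* + 8. The number begun by then is 6 + 8/*d*, counting one who starts that day.

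| *d* (weeks, assumed) | Begun | Of the 14, begun | Not begun |
|---|---|---|---|
| 4 | 8 | 2 | 12 (60%) |
| 2 | 10 | 4 | 10 (50%) |
| 1 | 14 | 8 | 6 (30%) |

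Those already begun might have forms on file at the sixth-patient review, if that review covers ongoing participants. Those not begun cannot. Only the figure of 14 comes from the documents; the split depends on the assumed rate.

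**3. Where each kind of information goes.**

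| Information | Individual use, throughout | Stated route to the Monitor after the sixth completer |
|---|---|---|
| Serious adverse events | Elicited at each visit (3.e.14) | Yes, immediate (6.e) |
| Non-serious adverse events | Elicited at each visit (3.e.14) | None |
| SSI | To the psychiatrist at the visit (6.d, item 3); 6-point rise shared with family (6.d, item 6) | None |
| Blood pressure | Each visit (3.e.11); limits on dose increases (3.e.4) | None |

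**4. What a later look could add (illustration only).** With 1:1 allocation in blocks of two, take 3 prazosin patients among the first 6 completers and 10 among all 20. For an assumed per-patient rate *p* of a non-serious event, P(at least 2) = 1 − (1 − *p*)^*n* − *np*(1 − *p*)^(*n* − 1).
- *p* = 10%: 2.8% with *n* = 3; 26.4% with *n* = 10.
- *p* = 20%: 10.4% with *n* = 3; 62.4% with *n* = 10.

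This assumes that only completers' forms are seen at the sixth-patient review. The finding does not depend on it.

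**5. Check of the proposed schedule.** Reviews at 3, 6, 9, 12, 15 and 18 are 3 apart, and 20 − 18 = 2 finish after the last. With no withdrawals, the 18th finishes at week 17*d* + 8 and the 20th starts at week 19*d*. The 20th has begun by then when 19*d* ≤ 17*d* + 8, that is, *d* ≤ 4 (at *d* = 4, both fall in week 76). With slower entry the 20th has not begun. The fix should therefore not assume that everyone is in treatment at the 18th-participant review.

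**The case against.** The strongest reply is that this is a deliberate, front-loaded plan for a pilot of 20 with a marketed drug whose cardiovascular effects the protocol describes as fully characterized. Two early looks are followed by open-ended reporting of serious events. Every participant is seen weekly by a psychiatrist (6.g), with blood pressure at each visit and clear means of individual action. No section contradicts another, and no section promises more reviews. More reviews without a criterion for a systematic rise in risk may change no decision.

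Much of this stands. It is a gap in design and not an internal contradiction, the individual safeguards are real, and the missing criterion is a genuine limit of the fix. None of it supplies the Monitor with a scheduled cross-participant view after the sixth completer. Section 6.e says that the Monitor has no other relationship with the study, so the view is unlikely to arise by another route. The plan gives no reason why forms worth reviewing for the first six are not worth reviewing for the rest.

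Four stronger readings are tempting, and the documents do not support them.
- That 70% of the safety data goes unseen. Some of the 14 may be in treatment at the sixth-patient review, and the accrual rate is unknown.
- That the Monitor alone can end the trial. Section 6.d makes the Monitor's determination a necessary condition. It does not say who carries out termination, or that the determination can arise only at a scheduled review.
- That later review is ruled out. An ad hoc request is neither planned nor forbidden, and the third and sixth might have been meant as the start of a repeating series, though nothing written says so.
- That participants are unprotected after the sixth completer. Sections 3.e.4, 3.e.11, 6.d and 6.g show otherwise.

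**Conclusion.** The point holds as a gap in trial-level oversight. The plan ties early termination to the Monitor's determination, but schedules the Monitor's form reviews only up to the sixth completer. After that, the sole stated input is serious adverse events. Up to 14 of 20 participants (70%) finish after the last scheduled review, or 11 to 13 if one to three are withdrawn first.

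The 14 rests only on the stated sample size and schedule. The 6 to 12 participants not yet begun at that review rest on assumed even entry at one per 1 to 4 weeks with no withdrawals, and should be read as a range, not an estimate. The change is worth making because it is cheap and bears on participant safety. The documents do not show that a signal would be missed.

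**What to change.** In 6.e, keep the third and sixth reviews and add three statements:
- reviews continue after every third participant, for example the 9th, 12th, 15th and 18th, for as long as any participant remains to be enrolled or is in treatment;
- the count includes participants who complete and those who are withdrawn;
- each review covers all SSI, vital-sign and adverse event forms collected to date, including those from withdrawn and ongoing participants.

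The cost is two or three sentences and about four more short reviews by the existing Monitor, with no new data or staff. With 20 participants, no more than 3 leave between reviews and at most 2 finish after the 18th-participant review.

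Two matters stay outside this change. It gives the Monitor the input for judging a systematic rise in risk, but not the criterion. Separately, the SSI collection times must be reconciled: 3.e.5 lists baseline and weeks 1, 2 and 4 of randomized treatment, while 6.d, item 3, has the SSI at each scheduled visit and 6.g has it weekly. That conflict affects how many SSI forms a review would contain, but not the finding itself.

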#### 3.e.5. Measurement of Suicidal Ideation and Behavior

The Scale for Suicide Ideation (SSI) consists of 19 items that evaluate active suicidal desire, specific plans for suicide, and passive suicidal desire.{Beck, 1979 18 /id;Beck, 1997 19 /id;Beck, 1999 20 /id} Each item is rated by the patient on a 3-point scale from 0 to 2 for a maximum score of 38; a lower score indicates less severe suicidal ideation. The SSI will be collected at baseline and at weeks 1, 2, and 4 of randomized treatment, and once by telephone one month after completing randomized treatment. An SSI score >2 predicts increased risk for suicide death over a period of years.{Brown, 2000 314 /id} The SSI will be collected at the start of each visit, before the participant is seen by the study psychiatrist.

The Columbia-Suicide Severity Rating Scale (C-SSRS){Oquendo, 2003 1195 /id} is based upon the Columbia Classification Algorithm of Suicide Assessment(C-CASA).{Posner, 2007 932 /id} This C-SSRS is used by the FDA in clinical trials to assess suicide risk, and includes a structured assessment of past or recent suicidal behavior. It will be administered at each visit by a study psychiatrist blinded to treatment assignment. C-CASA has excellent inter-rater reliability in classifying suicide attempts, with an overall intra-class correlation coefficient of 0.89.

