## 6. PROTECTION OF HUMAN SUBJECTS

### 6.a Subject selection procedures

The subject selection features of REST-ON-PTSD are intended to: (1) yield a sample with PTSD associated with suicidality, and (2) exclude patients who might be harmed by exposure to psychotropics, including pregnant women. Three procedures are used to assure participant safety at the baseline assessment: the Mini Mental State Exam (MMSE),{Folstein, 1975 78 /id} a pregnancy test for women of conception age, and a baseline Columbia- Suicide Severity Rating Scale (C-SSRS) score.

A MMSE score < 24 is statistically abnormal at any age and is consistent with global cognitive deficits such as seen in dementia.{Crum, 1993 313 /id}

All women of child bearing age will complete a urine pregnancy test at the first face to face visit. Persons excluded because of overly intense suicidal ideation (C-SSRS suicidal ideation score >3) will be evaluated for safety and perhaps the need for psychiatric hospitalization.

The additional subject exclusion factors are:

- History of sensitivity or allergy to prazosin or quinazolines
- History of fainting or syncopal episodes in the last 6 months
- History of hypotension
- Automatic Blood Pressure readings with systolic BP <90, or diastolic <50, either sitting or standing.
- Planned use of sildenafil, tadalafil, or similar erectile dysfunction medication

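### The Medical Monitor's stated inputs omit the C-SSRS, so an on-study ideation score of 4 or more that is managed without hospitalization and not recorded as an AE has no required route to the Monitor

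*Combined protocol and SAP*

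**What the plan says.** Section 6.e sets out what the Medical Monitor receives. "All serious adverse events (SAEs) will be reported immediately to" the Monitor, who otherwise "will review the case report forms for the Scale for Suicide Ideation, vital signs, and AEs after the third and sixth patients are completed". The C-SSRS appears in neither list.

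Elsewhere the C-SSRS has a larger part. Section 6.d item 3 states: "At each scheduled study visit, the protocol will quantify suicidality 2 ways". The two ways are the SSI, completed by the participant, and the C-SSRS. Section 3.e.5 says of the C-SSRS: "It will be administered at each visit by a study psychiatrist blinded to treatment assignment". The scale also caps entry. Sections 3.e.3 and 6.d item 1 require an ideation score of 3 or less, and item 1 comments: "This range defines patients with mild and moderate suicidal ideation, but with no intent to commit suicide". Section 6.a provides that people excluded because of "overly intense suicidal ideation (C-SSRS suicidal ideation score >3) will be evaluated for safety". Section 6.d item 7 equates a score below 4 with not normally meeting criteria for emergency psychiatric admission.

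For a participant who worsens on study, section 6.d item 3 gives the study psychiatrist a range of responses: patients judged to be at increased risk "will have an increased frequency of research visits, have smaller supplies of research medication, or may be withdrawn from the study and possibly hospitalized". On early stopping, section 6.d item 9 says that "the trial would be terminated prematurely only if the Medical Monitor determined that there was a systematic increase in risk".

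**The concern.** Every participant enters with a C-SSRS ideation score of 3 or less, so any later score of 4 or more crosses the protocol's own line. The SSI criterion is a floor of 3 with no ceiling, which leaves the C-SSRS as the only numeric upper bound. The person who must judge whether risk is rising across the trial is not assigned the scale that defines that bound.

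What is at stake is pattern detection. Safety is a stated tertiary aim, the sample is suicidal by design, and the Monitor's judgement is the sole stated ground for early termination. A study psychiatrist can treat each patient well while nobody with stopping authority sees that several patients have crossed the same line.

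**Working it through.** The plan gives no figure to reproduce. The check is to follow a post-baseline C-SSRS ideation score of 4 or more through each route by which the documents could carry it to the Monitor.

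1. **As a form at a scheduled review (6.e).** The list is SSI, vital signs and AEs. There is no C-SSRS form, so this route is absent.

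2. **As an SAE (6.e).** This route is immediate. If the score led to hospitalization it would probably be reported, and 6.d item 7 makes hospitalization a natural consequence of such a score. But 6.d item 2 leaves hospitalization to the psychiatrist's global clinical judgement, and item 3 allows extra visits, smaller drug supplies or withdrawal instead. No section defines an SAE or says that an ideation score is one. The route is likely in severe cases but not required.

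3. **As an AE (3.e.14, then 6.e).** Section 3.e.14 relies on spontaneous reports and applies C-SSRS coding to potentially self-injurious behavior. It does not mention the ideation level. Self-injury is therefore covered; ideation alone is not required to be entered. A non-serious AE also reaches the Monitor only at the two scheduled reviews.

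4. **As a rise in the SSI (6.d item 6, 6.h.1).** A 6-point rise is defined as emergent ideation. The stated consequence is telling the participant of the intent to inform family. Notice to the Monitor is not mentioned.

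5. **Through the SSI forms (6.e).** These do reach the Monitor, after the third and sixth patients complete. No section maps an SSI total to a C-SSRS level. How much the SSI can stand in for the C-SSRS also depends on a schedule that the documents state in two ways:
   - Section 3.e.5 lists post-baseline SSI during treatment at weeks 1, 2 and 4. The C-SSRS is given at all 8 weekly visits. Visits with a C-SSRS but no SSI: 8 − 3 = 5 of 8 (weeks 3, 5, 6, 7 and 8).
   - Sections 3.f, 6.d item 3 and 6.g imply weekly SSI. Visits with a C-SSRS but no SSI: 8 − 8 = 0 of 8.

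   The range is 0 to 5 of 8 visits per participant. If 3.e.5 governs, the C-SSRS is the only suicidality scale scheduled in weeks 5 to 8. The suicide item of the depression scale also stops at week 4 (3.e.7). Table 1 reaches its highest permitted doses in weeks 5 and 6.

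**What is left over.** Routes 2 and 3 cover hospitalized cases (probably) and self-injury. Route 5 gives partial cover at two time points. The uncovered case is a score of 4 or more that is managed without hospitalization and not recorded as an AE.

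**The case against.** The strongest reply is that the protocol divides the labour sensibly. Ideation intensity is the SSI's job, and SSI forms go to the Monitor. Self-injury is the C-SSRS's job, and it is placed in the adverse-event section, which feeds the Monitor. The study psychiatrist who gives the C-SSRS also elicits AEs and SAEs, so a marked worsening is known to the person making those entries. By the protocol's own equation in 6.d item 7, a score of 4 or more normally points to emergency admission, hence probably to an SAE. Section 6.e does not say its list is exclusive, and nothing commits the sponsor to sending the Monitor every instrument.

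Much of this stands. It makes the gap narrow and shows that no two sections contradict each other on this point. It does not close the gap. Section 6.g describes both scales as assessments of ideation, so the division is not clean. Nothing obliges the psychiatrist to enter a raised ideation score as an AE. The SAE route depends on a judgement and on an undefined term.

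Three stronger readings are tempting, and the documents support none of them:

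- *The Monitor is blind to suicidality.* The Monitor gets SSI forms, AEs and all SAEs.
- *Participants are unprotected.* Sections 6.d and 6.g provide weekly psychiatric review informed by the C-SSRS, with withdrawal and hospitalization available.
- *The size of the gap is the 14 of 20 participants who complete after the last scheduled review (20 − 6 = 14).* That count reflects when reviews happen. It would apply equally to vital signs, which are on the list, so it does not measure the omission of the C-SSRS.

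**Conclusion.** The point holds in a limited form and is minor. As written, a post-baseline C-SSRS ideation score of 4 or more that does not lead to hospitalization and is not recorded as an AE need not reach the only person who can stop the trial. This is a cheap improvement to trial-level oversight. It is not an error in the analysis or a failure of individual care.

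The documents give no frequency for scores of 4 or more, so none is claimed. The conclusion assumes that the 6.e list is what the Monitor will actually be sent, and that no SAE definition outside these documents captures ideation scores. If such a definition exists and applies, the immediate-notice part of the gap closes. If the SSI is in fact collected weekly, the Monitor's partial view is better than the 3.e.5 schedule suggests, but the route is still not required.

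**What to change.** In section 6.e:

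1. Add the C-SSRS forms to those the Monitor sees at the scheduled reviews.
2. Require prompt notice to the Monitor of any post-baseline C-SSRS ideation score of 4 or more, throughout the trial and so including the period after the sixth patient completes.

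Leave the 6-point SSI definition in 6.d item 6 and 6.h.1 as it is, and leave individual management with the study psychiatrist. No added analysis or stopping boundary is needed.

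The cost is one or two sentences. The scale is already given at every visit, so no new data or visits are required. The downside is a few extra notices to the Monitor.
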